If you are a woman capable of becoming pregnant, we will ask you to have a pregnancy test before beginning this study. You must use effective birth control methods and try not to become pregnant while participating in this study. If you become pregnant, there may be unknown risks to your unborn child, or risks to your unborn child that we did not anticipate. There may be long-term effects of the treatment being studied that could increase the risk of harm to an unborn child. You must tell the doctor if your birth control method fails while you are on the study. If you believe or know you have become pregnant while participating in this research study, please contact the research team member identified at the top of this document as soon as possible. Please discuss with the research team how long you need to wait before becoming pregnant after completing the treatment or procedures on this study.

If you are a sexually active male it is important that your partner not become pregnant during your participation in this study. There may be unknown risks to the unborn child or risks we did not anticipate. You and your partner must agree to use birth control if you want to take part in this study. If you believe or know that your partner has become pregnant during your participation in this study, please contact the research team member identified at the top of this document as soon as possible.

LOCATIONS / SITES OF STUDY

Data collection: Washington University School of Medicine

Data analysis: Washington University School of Medicine

STUDY DURATION

Anticipated duration of entire research activity per patient:

- Aim 2: Three days over the course of 1½ to 3 months*
- Patients not in Aim 2: Two days, which can occur up to a few weeks apart*

* One additional make-up scan day will be allowed for each subject, with his/her consent, in the event of technical problems that prevent completion of the scan day procedures. MRI equipment failure or a broken infusion pump are examples of such technical problems.

Anticipated duration of entire research activity:

Three years

SAMPLE SIZE

Aim 1: N = 20

Aim 2: N = 10 (up to 2 subjects can overlap between groups)

The N's above refer to subjects who are eligible after screening procedures and who continue in the study. Additional subjects may be screened to reach this number of eligible subjects.

Power considerations: For a first study of a method, there is no information available to confidently

predict variance of the key outcome measures and provide a formal power analysis. We have chosen the sample sizes here pragmatically, to allow recruitment and scanning at a steady, practically achievable rate. We note that the sample size of 20 for Aim 1 provides power >80% to find a moderately strong positive correlation ($r = 0.5$) while maintaining a low false positive rate $\alpha=0.05$. Power exceeds 99% to find a very strong correlation that would explain half the variance in disease severity ($r = 0.7$).

Additional levodopa-naïve subjects would not help Aim 1 substantially, as a Pearson correlation analysis is not appropriate if a large fraction of subjects are lumped at one end of the range of disease duration or severity. Therefore we plan to limit to 2 the number of subjects included in both Aims. However, if severity or duration vary substantially among the never-treated subjects, we may include more than two of them in the Aim 1 analysis. The number of subjects for Aim 2 is largely pragmatic, given the difficulty of recruitment and the additional cost with 2 scans per subject.

INCLUSION CRITERIA

There are two groups of subjects. All have idiopathic Parkinson disease. For the first group, we will attempt to sample a broad range of severity and disease duration. The second group will not be treated currently with levodopa, so most subjects in this group will be early in the disease process.

Inclusion criteria for all subjects:

- Age 40-79 at screening
- Meet accepted diagnostic criteria for Parkinson disease

EXCLUSION CRITERIA

Exclusion criteria for all subjects:

- Pregnancy
- Metal in the head or eye, or other contraindication to MRI
- Deep brain stimulator (DBS)
- Patients taking a dopamine antagonist or dopamine partial agonist
- Claustrophobia
- Significant neurologic disease other than PD (exceptions would include febrile seizures or uncomplicated migraine)
- Head trauma with loss of consciousness for more than 5 minutes
- Severe or unstable systemic illness
- MMSE < 24
- History of a primary psychotic disorder
- Current severe major depressive episode (clinical diagnosis after psychiatric interview)
- Current alcohol use disorder (clinical diagnosis after screening with the Michigan Alcoholism Screening Test)
- Current psychosis
- Subjects who feel that going without nicotine for 3-4 hours would be uncomfortable
- Currently taking an extended-release formulation of a dopamine agonist

Additional exclusion criteria for Aim 2 subjects:

- Taking levodopa currently or in the past month, or ever for more than a month
- Taking a dopamine agonist currently

CONCOMITANT MEDICATIONS

Required:

- none

Allowed:

- Most drugs that do not prominently affect the brain or constrict blood vessels
- Loratadine and other non-sedating antihistamines
- Benzodiazepines or “Z drugs” with short half-life used in the evening only
- Medications taken only as needed (less than daily), except those listed below

PROHIBITED MEDICATIONS

Daily use of any of the following medications:

- medications containing caffeine or theophylline
- benzodiazepines with long half-lives (e.g. clonazepam), except that a single dose at bedtime for treatment of REM sleep behavior disorder may be allowed at the discretion of the PI
- centrally-active antihistamines or anticholinergics (e.g. Benadryl®)
- orally administered nasal decongestants

If taken in the 24 hours prior to the MRI scans:

- p.r.n. benzodiazepines with long half-lives, p.r.n. Benadryl®, illicit drugs

If taken on the morning of the MRI scans:

- antiparkinsonian medications
- stimulants, nasal decongestants, caffeine, nicotine, alcohol

TREATMENTS AND DOSAGE

MRI Scan day

Treatments:

- Carbidopa (Lodosyn® 25mg tablets), or FDA-approved generic equivalent
- Levodopa 2mg/ml in normal saline, as described in previous IND communications, supplied by the Barnes-Jewish Hospital Research Pharmacy service

Dose:

Carbidopa: 200mg = 8 × 25mg tablets by mouth at least 1 hour before starting the levodopa infusion

Levodopa solution: based on age and body mass as follows:

Loading dose: 0.6426mg / kg / (10 min.)

Maintenance rate: 2.882 mg/kg/min. × 10⁻⁵ × (140 year – age)/year

This is the “final dose” in Table 1 [15]. The total levodopa dose for a 60-year-old 70kg subject over a 2.5-hour infusion is 68mg; an oral dose of 80 mg would provide the same total absorbed dose, though

over a slower time scale [17]. We have used this method with the 200mg carbidopa in previous studies and reported on its safety [13,18].

Oral treatment between scan days, in the Aim 2 group

Treatment:

- Carbidopa/levodopa 25/100mg tablets (Sinemet® or FDA-approved equivalent)

Dose:

Individualized for each subject based on response (benefits and side effects). Generally the starting dose will be ½ tablet by mouth twice daily, with dose increases or reductions based on contacts with the subjects as needed. Supplemental carbidopa will be prescribed for patients with prominent non-CNS side effects who have inadequate motor response (or are expected to if the dose is lowered). The plan will be not to change the dose, except for urgent clinical need, during the week prior to the second MRI scan day. See Appendix.

ANALYSIS PLAN/APPROACH/METHODOLOGY

Outcome measures

There are no outcome measures relevant to clinical care. This is not a treatment study.

Data analysis

Neuroimaging data analysis will begin with routine data preprocessing steps. ASL images will be converted to rCBF images using our previously described methods [19], weighted inversely for head motion similar to the approach of [20]. A Bayesian parameter estimation [21] procedure, with the addition of a hysteresis parameter k_e as described in Objectives above, will then be applied to repeated serum levodopa concentrations, and time–CBF curves from the volumes of interest (VOIs) listed below to estimate k_e for each VOI.

Thalamus and striatal nuclei (putamen, caudate, nucleus accumbens) will be defined from each participant's structural MR image(s) using the method of ref. [22], or if needed by FreeSurfer (<http://surfer.nmr.mgh.harvard.edu/>). Alternatively, the structures can be defined manually from the mean group atlas-aligned MPRAGE image. VOIs will be defined independent of any clinical data.

Primary VOIs:

1. Midbrain (MB). This VOI will be defined from the group difference image comparing the mean rCBF image from approximately 15-40' after the start of the LD infusion to the mean pre-infusion baseline rCBF image. The 15-40' time frame is expected to reflect activation from LD in nearly all subjects (see Fig. 2). The same time frame will be used in all subjects. The VOI will be masked to exclude voxels outside the brain. The VOI may extend into pons; comparisons to published results from 2DG and PET studies will guide any questions about defining the borders of the VOI.
2. Posterior putamen VOIs from each side of the brain (LpP, RpP). On each axial slice, a line normal to the sagittal plane and tangent to the fornix posteriorly will divide the anterior and posterior putamen, as in ref. [23]. The nucleus accumbens is excluded.

Secondary VOIs:

3. Left and right caudate VOIs (LC, RC).
4. Left and right anterior putamen (LaP, RaP) as defined above. The nucleus accumbens is excluded.
5. Left and right nucleus accumbens (LNA, RNA).
6. Thalamus (Th).
7. Each voxel in the brain.

The primary analysis will be a correlation across all Aim 1 subjects of the k_e 's for a VOI to clinical measures of disease severity and duration. Duration of illness will be measured from the first symptom, as recorded on the screening day. Standard 20cm tapping speed in the L and R hand and hemi-UPDRS part III motor scores, both measured in the standard off condition, will capture the increased variance provided by clinical asymmetry and will be correlated with contralateral posterior putamen k_e . Midbrain k_e will be compared to total "off" UPDRS part III scores and tapping speed in the more affected hand. Specifically:

The primary comparisons for Aim 1 will be simple Pearson correlations:

1. between the off-period 20cm tapping speed in the more affected hand and the midbrain k_e , and
2. between the off-period total UPDRS part III motor score and the midbrain k_e .

Secondary comparisons for Aim 2 will be correlations:

3. between "off" 20cm tapping speed on each side and contralateral posterior putamen k_e , and
4. "off" hemi-UPDRS part III motor scores on each side and contralateral posterior putamen k_e .

For #3 and #4, we will calculate the r values using repeated measures correlation [24], with side as the repeated measure, rather than as $2n$ independent data points. However, we are interested in between-subject correlation as well as the within-subject r_{rm} that the `rmcorr` package focuses on, so we will also report that p value (corresponding to the first row in Table 3 of ref. [24]).

For Aim 2, the k_e 's for each VOI will be compared before and after 6 weeks of treatment in a repeated measures ANOVA analysis. Here the key comparison is whether k_e changes with time (before vs after treatment) in any VOI, controlling for side (more affected side vs less affected side). Our hypothesis is that this change with time is at or near 0, so our answer will be framed in terms of 95% confidence intervals for change. Any VOIs identified from the Aim 1 SPM analysis will also be tested.

Secondary analyses will correlate k_e 's from secondary VOIs to all measures of disease severity (off tapping speed, off UPDRS III, disease duration) and to cognitive test scores (NIH Toolbox task scores adjusted for age), using the off-period scores for measures done on the scan day. Voxelwise analyses will use SPM with an initial threshold of $t \geq 3.0$ and statistical inference at the cluster level with a false discovery rate of 0.05. Another secondary analysis will use the k_e computed from the button box tapping speeds from the more affected hand and the levodopa concentrations, independent of the perfusion MRI data ("tapping k_e "). We will test whether the tapping k_e correlates with the k_e from the midbrain or contralateral posterior putamen, or other VOIs.

Note that we expect that k_e for some VOIs will correlate better than for other VOIs with measures of disease severity or duration. This conclusion is based on the expectation that a specific clinical effect may be better associated with dopamine buffering capacity in a specific (set of) brain region(s).

Therefore we expect that the k_e -vs-clinical slope may differ significantly from zero only for a subset of the VOIs; in other words, we do not expect the slopes to be parallel across VOIs, and therefore will not include all VOIs in a single ANCOVA with a factor for VOIs. However, any errors in estimating pharmacokinetic parameters (i.e., in reconstructing the continuous function $C_p(t)$, plasma levodopa concentration as a function of time for $t \geq 0$) occur at the subject level. Such errors will affect all k_e estimates for that subject (i.e., across all VOIs). Therefore we cannot assume independence across VOIs, within subject, for the measured estimates of k_e .

Visual analog scale (VAS) measures of side effects will be analyzed as repeated measures ANOVAs. Other variables (demographics, clinical measures, NIH Toolbox scores, etc.) will be summarized or compared as appropriate using standard statistical methods.

Additional analysis details

We will examine interactions of the key analyses with subject demographics or disease variables such as age or presence of dyskinesias.

We will use a $p=.05$ threshold for significance tests. All the correlation hypotheses are one-sided, i.e. k_e will increase with increasing disease severity or duration (e.g., positive correlation for UPDRS scores or duration, as in Fig. 1 of the attached protocol; negative correlation for tapping speed). We will not correct for multiple comparisons among the 4 numbered primary analyses named above. The secondary analyses described above involve a number of comparisons but are exploratory. We will correct individual voxelwise analyses for multiple comparisons using SPM, as described above.

For the primary analyses (correlations of k_e and disease severity or duration), outliers will be determined at the level of the individual variables before computing the correlations. If the distribution of k_e values or of disease severity markers clearly deviates from a normal distribution on visual inspection because of outlying values, after transformation if appropriate, we will use a nonparametric analysis such as a Spearman correlation.

Subjects without “off” tapping score or UPDRS will be excluded from the pertinent analyses.

Subjects without a k_e value, due to missing perfusion MRI data or missing [LD] data, will be excluded from the primary analyses. However, subjects with a few missing [LD] data points that do not prevent a good fit to the PK model will be included; an example may be a subject with missing [LD] values only between (say) 30 and 90 minutes after the infusion starts.

SAFETY MONITORING

We have recently summarized the world literature on safety of *i.v.* levodopa and no SAEs are expected [16].

The Data Safety Monitoring Plan for this protocol will consist of the following measures:

- The PI will monitor for unanticipated problems, life-threatening events and deaths.
- We will report adverse events to the Washington University Human Research Protection Office (HRPO), and in annual reports to the sponsor and the FDA.

If any SAE occurs that is judged to be probably or definitely related to participation in the study, enrollment will stop until restarting is approved by the HRPO.

REFERENCES CITED

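### With 20 subjects, the Aim 1 one-sided Pearson test has about 76% power at r = 0.5 and 98% at r = 0.7, not the stated >80% and >99%.

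*Combined protocol and SAP*

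**What the plan says.** Under SAMPLE SIZE, Aim 1 is set at N = 20. That number counts subjects who pass screening and continue in the study. The power paragraph says that a formal power analysis is not possible for a first study of the method and that the numbers were chosen pragmatically. It then gives two figures at alpha 0.05. For r = 0.5, "the sample size of 20 for Aim 1 provides power >80% to find a moderately strong positive correlation". For r = 0.7, "Power exceeds 99% to find a very strong correlation that would explain half the variance in disease severity". It names neither the method nor the sidedness.

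The analysis plan supplies the rest. Under Data analysis, the primary Aim 1 comparisons are Pearson correlations of midbrain k_e with off-period 20 cm tapping speed in the more affected hand and with the off-period total UPDRS part III score. Under Additional analysis details, the significance threshold is 0.05, "All the correlation hypotheses are one-sided", and the numbered primary analyses are not corrected for multiplicity. Subjects with no k_e "will be excluded from the primary analyses", and those lacking the off tapping score or UPDRS drop out of the analyses that need them.

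**The concern.** Both figures are strict lower bounds, and the documents contain every input needed to check them except a distributional assumption. The usual assumption for Pearson power is bivariate normality. A quick Fisher z calculation on that basis falls below both bounds even with the more favourable one-sided test.

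These two figures are the only quantitative support given for N = 20. The study aims to validate k_e as a measure of severity and to position it as a surrogate endpoint, so a null result would be read against the stated power. If that power is too high, a null result would look like stronger evidence against the method than it is.

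**Working it through.** **Inputs.** n = 20, r = 0.5 and 0.7, and alpha = 0.05 (SAMPLE SIZE, power paragraph); Pearson test (Data analysis); one-sided with no multiplicity correction (Additional analysis details). Bivariate normality is my assumption.

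**Critical value.** With 18 degrees of freedom the one-sided 5% point of t is 1.734. The critical correlation is 1.734 / √(1.734² + 18) = 0.378.

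**Trying to reproduce the plan's figures.** The plan names no method, so I tried the common ones.

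- *Fisher z.* Power = Φ(atanh(r)·√(n − 3) − 1.645).
  - r = 0.5: 0.5493 × 4.1231 − 1.645 = 0.620, power 73.2%.
  - r = 0.7: 0.8673 × 4.1231 − 1.645 = 1.931, power 97.3%.
- *One variable treated as fixed.* Noncentral t with noncentrality √20 · r / √(1 − r²).
  - r = 0.5: noncentrality 4.472 × 0.5 / 0.8660 = 2.582, power 79.9%.
  - r = 0.7: noncentrality 4.472 × 0.7 / 0.7141 = 4.384, power 99.5%.
- *Normal approximation to the fixed-variable form.* At r = 0.5, Φ(2.582 − 1.645) = 82.6%; at r = 0.7, 99.7%. Of the methods tried, only this one exceeds both stated bounds. It does so by replacing the t distribution on 18 degrees of freedom with a normal, so it is not the power of the planned test.

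**Exact power of the planned test.** When both variables are random, the noncentrality is r / √(1 − r²) · √V, with V chi-square on n − 1 = 19 degrees of freedom. Exact power is the noncentral-t power averaged over V. Integrating the exact density of the sample correlation above 0.378 gives the same values, and a simulation of 400,000 trials agrees (75.6% and 97.8%).

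| Method, n = 20, alpha 0.05 | r = 0.5 | r = 0.7 |
|---|---|---|
| Plan | >80% | >99% |
| Exact, one-sided | 75.6% | 97.8% |
| Fisher z, one-sided | 73.2% | 97.3% |
| One variable fixed, one-sided | 79.9% | 99.5% |
| Exact, two-sided (for reference; not the planned test) | 64.2% | 95.6% |

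Explaining exactly half the variance means r = √0.5 = 0.707, where exact one-sided power is 98.1%.

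**What would meet the stated floors.** Exact one-sided power at r = 0.5 is 79.4% with 22 subjects and 81.0% with 23, so 23 are needed. At r = 0.7 it is 99.0% to one decimal (98.95%) with 23 and 99.2% with 24, so 24 are needed. With n = 20, power reaches 80% at r ≈ 0.526 and 99% at r ≈ 0.736.

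**Loss of analysable subjects.** The documents give no loss rate. As an illustration only, 18 analysable subjects would give 71.2% and 96.6%.

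**The case against.** The best defence is that N = 20 was never derived from these figures. The protocol says the number was pragmatic and offers the power sentence as a remark. That is true, and it is why no change to the sample size follows. It does not make the two figures correct.

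A second defence concerns the model. The protocol intends to sample a broad range of severity, so severity is not a simple normal draw. If severity were uniformly distributed, simulated power is about 77% and 98.7%. If it were evenly spaced, which amounts to treating it as fixed, power is 79.9% and 99.5%. This has some force: the claim at r = 0.7 depends on the model and can be met under the most favourable one. The claim at r = 0.5 is met under none of these. The protocol also does not fix severity values by design; k_e, tapping speed and UPDRS are all measured.

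A third defence is that losses may be small. A make-up scan day is allowed for technical failures, subjects with a few missing levodopa concentrations are kept, and more than two never-treated subjects may join the Aim 1 analysis. These provisions limit the risk of falling below 20, and the last could raise the number. They do not guarantee 20 analysable subjects, and the shortfall exists at a full 20.

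Finally, a miss rate of 24% rather than under 20% changes the reading of a null result only modestly, since that reading would rest mainly on the observed correlation and its interval. I agree that the practical effect is modest.

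**Conclusion.** The concern holds. For the planned one-sided Pearson test at 0.05 with 20 analysable subjects and bivariate normal data, power is 75.6% at r = 0.5, which is 4.4 points below the stated floor. At r = 0.7 it is 97.8%, or 1.2 points below. The chance of missing a true correlation is therefore about 24% instead of under 20%, and about 2.2% instead of under 1%.

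The error at r = 0.5 is the firmer and more material one: it survives the Fisher z, exact, fixed-variable and spread-severity calculations. The error at r = 0.7 is small and disappears if one variable is treated as fixed. The design, the test and the number of patients are unaffected.

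**What to change.** Replace the two power statements with: *With 20 analysable subjects and a one-sided alpha of 0.05, the exact power of the Pearson correlation test under bivariate normality is about 76% for r = 0.5 and about 98% for r = 0.7; 80% power is reached at about r = 0.53.* Add that power would be about 71% at r = 0.5 if only 18 subjects were analysable, and label the 18 as an assumption.

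No extra patients are needed, because the protocol bases N on feasibility. If the sponsor prefers to keep the stated floors, the analysable N must be 23 for r = 0.5 and 24 for r = 0.7. The recommended change costs only protocol wording and a slightly less favourable power statement.

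### Does the option to bring more than two Aim 2 subjects into the Aim 1 correlations leave the 5% error rate unprotected?

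*Combined protocol and SAP*

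**What the plan says.** The Sample Size section sets N = 20 for Aim 1 and N = 10 for Aim 2, and adds that "up to 2 subjects can overlap between groups". The power paragraph gives the reason for a cap: a Pearson correlation is a poor tool when many subjects bunch at one extreme of duration or severity. Hence "we plan to limit to 2 the number of subjects included in both Aims". An exception follows: "if severity or duration vary substantially among the never-treated subjects", then "we may include more than two of them in the Aim 1 analysis".

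Under Data analysis, "The primary analysis will be a correlation across all Aim 1 subjects". The two primary comparisons for Aim 1 relate midbrain k_e to off-period tapping speed in the more affected hand and to the off-period total UPDRS part III score. Additional analysis details sets a 0.05 threshold and states that "All the correlation hypotheses are one-sided" and that "We will not correct for multiple comparisons among the 4 numbered primary analyses named above". The exclusions listed there are for missing data only. On the midbrain region, Primary VOIs says: "This VOI will be defined from the group difference image".

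**The concern.** The exception is permissive and its trigger is a matter of judgement. The plan does not say how much spread is enough, which Aim 2 subjects would enter, or when the decision is taken. Aim 2 needs k_e for all 10 of its subjects in any case, so every candidate's k_e will exist whether or not that subject joins Aim 1. If someone looked at the correlation with and without the extra subjects and kept the more favourable one, the nominal 5% would no longer hold for either primary test, and a reader could not tell from the plan whether this had happened. The study aims to validate a possible surrogate endpoint, so that doubt deserves a check.

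**Working it through.** **1. The plan's own figure.** For N = 20 and one-sided 0.05, the plan states power above 80% at r = 0.5 and above 99% at r = 0.7. With the noncentral t, ncp = √n · r/√(1 − r²) on n − 2 = 18 degrees of freedom:
- r = 0.5: ncp = 4.472 × 0.5/0.866 = 2.58, power 79.9%.
- r = 0.7: ncp = 4.472 × 0.7/0.714 = 4.38, power 99.5%.

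The statement is reproduced to within rounding on a one-sided, fixed-predictor basis. A simulated bivariate-normal Pearson test gives 75.6% and 97.9%. That is a separate matter, and the present point does not depend on it.

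**2. How large the set can be.** If two of the 20 are Aim 2 subjects, 18 are not. Adding all Aim 2 subjects gives 18 + 10 = 28. With no overlap among the 20, the ceiling is 20 + 10 = 30. The size of Aim 2 is therefore an implicit maximum.

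**3. Why a clinical trigger is harmless.** Suppose k_e is unrelated to the clinical measures and roughly normal. Given any set of severity values, the Pearson statistic t = r√(n − 2)/√(1 − r²) then follows a t distribution with n − 2 degrees of freedom. A rule that looks only at severity and duration picks among sets for each of which this holds, so the error stays at 5%.

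**4. Simulation.** Assumptions: 18 treated subjects with severity uniform on 0–1; 10 Aim 2 subjects with severity uniform on 0–0.4, 0–0.25 or 0–0.1; normal k_e unrelated to severity; one-sided 0.05; 1,000,000 trials per setting. The simulation standard error at 5% is √(0.05 × 0.95/1,000,000), about 0.02 points. The clinical trigger adds all Aim 2 subjects when the standard deviation of their severity is at or above its median.

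| How the set is chosen | 0–0.4 | 0–0.25 | 0–0.1 |
|---|---|---|---|
| Fixed, N = 20 | 5.02% | 4.97% | 4.99% |
| Fixed, N = 28 | 4.98% | 5.00% | 5.00% |
| Clinical trigger | 5.00% | 5.01% | 5.00% |
| Better of N = 20 and 28, after seeing k_e | 7.12% | 7.29% | 7.51% |
| Best of N = 20 to 28 in fixed order, after seeing k_e | 8.82% | 9.34% | 9.93% |

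The narrowest range sits badly with the trigger, because severity confined to a tenth of the treated range is not widely spread. With wider Aim 2 ranges (100,000 trials), the last two rows become 6.9% and 8.4% at 0–0.7, and 7.4% and 9.3% at 0–1.

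**5. What a rigid cap would cost.** In the same model at r = 0.5, with a linear relation and no treatment effect on k_e, power at N = 20 is 77.6%, 79.2% and 81.3% across the three ranges. At N = 28 it is 87.3%, 90.4% and 93.4%. The differences are 9.7, 11.2 and 12.1 points.

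**6. Likely order of events.** Duration is recorded at screening. Off-period tapping and UPDRS are recorded on the scan day before the infusion. Midbrain k_e needs a region drawn from a group image, so it is likely to come later. The clinical facts that the trigger uses are in hand first.

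**The case for a change.** The strongest case for a change is that the plan fixes the order of other choices but not this one. Regions of interest are to be defined without reference to clinical data, and outliers are to be judged before correlations are computed. Nothing comparable covers who is in the analysis. Posterior putamen k_e rests on individual anatomy and need not wait for a group image, so some k_e values could be seen early. A stricter reading goes further. If any pair of the 10 could be picked after the fact (45 pairs), the error would be 12.6% to 16.7% in the three ranges tabulated. If any subset of two or more could be picked (1,013 subsets), it would be 17.7% to 24.6%.

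The first part stands as a description: the timing is unwritten. The larger figures do not carry over to this plan. The allowance of up to two is a statement about sample size, most naturally read as group membership settled during recruitment, and neither it nor the exception offers a search over pairs or subsets. Those figures measure deliberate selection on the result.

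The obvious remedy is not clearly better either. Taking the first two by enrolment order ignores the spread of severity that Aim 1 wants. A compulsory analysis of all 28 would go ahead even when the Aim 2 subjects are bunched together, the case in which the plan calls a Pearson correlation unsuitable.

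**Conclusion.** The gap is real but small, and it is one that analysts fill sensibly: judge the spread on the clinical data, list the Aim 1 set, then fit k_e. Followed as written, the rule holds each one-sided test at 5%. An increase to about 7%, or to about 8% to 10%, requires a choice driven by k_e that the plan nowhere describes. These sizes rest on assumed uniform severity, normal k_e and 18 subjects outside Aim 2. The open wording has a stated statistical reason, and it preserves a possible gain in power in a first study of a method whose sample sizes are openly pragmatic. The reported N will also show whether the option was used. A line on timing would do no harm, but neither the design nor the analysis needs to change.
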